## 12.1.4. Additional Efficacy Analyses of the Primary Outcome: Adjusting for Clinical Centers (Tertiary Analysis)

Ideally, all prognostic variables used in the randomization scheme should be accounted for in the analysis of the primary efficacy outcome measure. For the POINT Trial, clinical center is included in the randomization scheme; as a result, clinical center should be accounted for in the analysis. However, due to the large number of participating centers (150), a statistical analysis model with center as a fixed effect would yield unstable estimates of the treatment effect, especially if some centers contribute a small number of subjects. Therefore, the center effect is omitted in the primary analysis of the composite event. However, as a secondary analysis, at the end of the study, we plan to analyze the primary efficacy outcome variable adjusted for clustering within center using a robust sandwich covariance matrix estimate to account for the intracluster dependence (proc phreg data=DATA covs(aggregate); id SiteID;). Sites with only 1 enrollment may be collapsed into a single category.

# 12.1.5. Additional Efficacy Analyses of the Primary Outcome: Adjusting for Geographic Region (Tertiary Analysis)

The geographic region of clinical site (classified as US vs Outside US) will be assessed.

# 12.1.6. Additional Efficacy Analyses of the Primary Outcome: Adjusting for Covariates (Tertiary Analysis)

For other exploratory analyses of the primary outcome variable, the composite event is assessed for treatment differences adjusting for a variety of covariates deemed clinically or prognostically important, such as age and time between symptom onset and randomization, whether a brain infarction is demonstrated on an initial scan. These adjustments are made in the form of a Cox proportional hazards model. Each covariate is evaluated individually first with a model that includes an interaction effect with the treatment (clopidogrel or placebo). If a significant interaction (p<0.10) is observed, subgroup analyses may be considered (see Section 12.1.7). Quantitative and qualitative interaction between the treatment and each covariate also are visually assessed by graphical methods. A multivariable model that includes covariates that contributed significantly (p<0.05) as treatment modifiers individually may then be constructed.

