### 12.4. Interim Monitoring Schematic

### 12.5. Secondary and Tertiary Clinical Efficacy Outcomes Analyses

### 12.5.1. Secondary Analyses

Several secondary analyses will be performed to evaluate of the impact of therapy. Prior to these analyses, univariate analyses of covariates, identified from previous studies as having confounding effect on the outcome measurements, are conducted to determine their inclusion in the multivariable models. In addition, stepwise regression methods may be applied to assess the best set of covariates to include in a particular model. Some of the suspected significant confounders are: age, time from symptom onset to randomization, African Americans, those previously taking aspirin, those with index TIA vs. minor ischemic stroke.

The usual verification of variable and model assumptions and goodness of fit assessments accompany each analysis. Time to event outcomes will be assessed via log rank test (unadjusted) and via cox proportional hazard model adjusting for covariates. A Wilcoxon log-rank test will be used for ordinal outcomes (mRS). A logistic regression will be used for binary outcomes (90 day mRS). The significance of each test is set at a two-sided alpha of 0.05.

ITT analyses and As-treated analyses will be performed for the following secondary outcomes for efficacy/net-benefit:

- Composite event of ischemic stroke, MI, ischemic vascular death, or major hemorrhage
- Ischemic stroke
- Ischemic vascular death
- MI
- Composite event of ischemic stroke and hemorrhagic stroke

ITT analyses and As-treated analyses for efficacy/net-benefit will be performed for the following secondary outcomes for safety/tolerability:

- Primary efficacy outcome from day 0 to 7 and day 8 to 90, and from day 0 to 30 and day 31 to 90 (HR and 95% CI will be calcuated via cox model for each time point stratified)
- Primary safety outcome from day 0 to 7 and day 8 to 90, and from day 0 to 30 and day 31 to 90 (HR and 95% CI will be calcuated via cox model for each time point stratified)
- All-cause Death
- Hemorrhagic stroke
- Symptomatic intracerebral hemorrhage
- Other symptomatic intracranial hemorrhage (SAH, SDH or IVH)
- Major Hemorrhage other than Intracranial Hemorrhage
- All minor hemorrhage (including asymptomatic intracranial hemorrhage)

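### The optional multivariable model in SAP 12.1.6 admits covariates on treatment interaction, not prognosis, so the section defines no clear covariate-adjusted hazard ratio

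*SAP*

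**What the plan says.** SAP 12.1.6 is headed as an adjustment for covariates, is labelled tertiary, and opens with "For other exploratory analyses of the primary outcome variable". Its purpose is that the composite is "assessed for treatment differences adjusting for a variety of covariates deemed clinically or prognostically important", with the examples "such as age and time between symptom onset and randomization, whether a brain infarction is demonstrated on an initial scan". The full list is not given.

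The procedure has three parts:

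- Each covariate goes into its own Cox model together with a treatment-by-covariate interaction.
- "If a significant interaction (p<0.10) is observed, subgroup analyses may be considered". The cross-reference points to 12.1.7, which is now the on-treatment analysis; subgroups are in 12.1.8.
- The rule for the joint model is: "A multivariable model that includes covariates that contributed significantly (p<0.05) as treatment modifiers individually may then be constructed".

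The section gives no criterion based on a covariate's own association with outcome and forces no covariate into the joint model. The primary analysis in SAP 12.1.3 is the unadjusted intention-to-treat log-rank test, with a Cox hazard ratio for estimation.

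**The concern.** The purpose and the entry rule do not match. Adjustment calls for covariates that predict the outcome. The rule asks whether the treatment effect differs across levels of the covariate. A strong predictor that acts equally in both arms fails that test by design.

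The trial expects such predictors. Protocol 2.6.1 reports 90-day stroke risk running from under 1% to 20% across ABCD² scores, and age is one component of that score.

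Two things are at stake. First, a reader of the trial report may take a result labelled as adjusted to account for the named prognostic factors when it accounts for none of them, or only for one that passed an interaction test by chance. Second, the content of the model depends on outcome data by arm. Protocol 10.1 says the SAP will define all pre-specified, planned analyses; a model chosen this way is not fixed in advance.

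**Working it through.** **Inputs.** Entry threshold: interaction p<0.05 (SAP 12.1.6). Covariates named: three (12.1.6); five is used as a second value because SAP 12.5.1 lists five suspected confounders. Events 530, hazard ratio 0.75, power 90%, placebo proportion 15.24%, inflation 5.0% (SAP 5.1). Final-look alpha 0.0463 (SAP Table 2). Assumptions: independent covariates; for the power figures, binary covariates with events split 50/50.

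**1. The plan's own figure.** The SAP gives no figure for how often a covariate is retained. The event target, used in steps 4 and 5, can be checked.

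- Freedman: ((1+0.75)/(1−0.75))² × (1.960+1.282)² = 49 × 10.51 = 515 events at alpha 0.05, and 526 at 0.0463.
- Schoenfeld: 4 × 10.51/(ln 0.75)² = 508, and 519 at 0.0463.
- Sample size: the treated proportion is 1 − 0.8476^0.75 = 0.1166 and the mean proportion 0.1345, so 530/0.1345 × 1.05 ≈ 4,137, against 4,142 stated.

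The figure of 530 is reproduced within 3% by Freedman at either alpha and by Schoenfeld at 0.0463.

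**2. No true interaction.** Each covariate passes with probability 0.05 and is left out with probability 0.95, whatever its main effect. The joint model is empty with probability 0.95^k:

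| Covariates (k) | P(none retained) |
|---|---|
| 3 | 85.7% |
| 5 | 77.4% |
| 10 | 59.9% |
| 13 | 51.3% |
| 14 | 48.8% |
| 20 | 35.8% |

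**3. Check by simulation.** In 1,320 simulated Cox trials there were three independent binary covariates, each with a prognostic hazard ratio of 2 and no interaction, and about 553 events per trial. A covariate was retained 5.2% of the time, and none was retained in 85.4% of trials. The main effect was tested for one of the three and was significant in every trial.

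**4. True interaction.** For a ratio r of the hazard ratios in the two covariate levels, SE(ln r) = √(4/265 + 4/265) = 0.174. P(retained) = Φ(|ln r|/SE − 1.96) + Φ(−|ln r|/SE − 1.96).

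| r | P(retained) | P(left out) |
|---|---|---|
| 0.9 | 9.3% | 90.7% |
| 0.8 | 25.0% | 75.0% |
| 0.75 | 38.1% | 61.9% |
| 0.67 | 63.5% | 36.5% |
| 0.5 | 97.9% | 2.1% |

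**5. Contrast with a prognostic criterion.** Suppose entry depended on the covariate's main effect at p<0.05. With 530 events, P(retained) ≈ Φ(|ln HR| × √(530 × 0.25) − 1.96). That gives 73% at a prognostic hazard ratio of 1.25, 99.7% at 1.5 and over 99.9% at 2.

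**6. What the one-covariate models estimate.** With treatment T and covariate X, the model is ln h(t) = ln h₀(t) + bT + cX + dTX. The treatment hazard ratio is exp(b + dX), so exp(b) is the effect at X = 0. For uncentred age that is age zero. It is not an overall adjusted effect. The SAP does not say whether interaction terms carry over into the joint model. If they do, the same reading applies there.

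**7. What adjustment would gain.** A logistic simulation used 5,840 patients, about 10% events and five binary covariates with assumed odds ratios of 1.3 to 2.0. The mean treatment |Z| was 3.223 unadjusted and 3.269 with all five entered. (3.269/3.223)² = 1.029, about 3% more information.

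**The case against.** The strongest reply is that little depends on this. The model is optional, tertiary and exploratory. No decision rule uses it, SAP section 9 rests the trial on the primary analysis, and the SAP nowhere calls 12.1.6 the test of whether the primary result survives adjustment. All of that stands and limits the weight of the point.

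Three stronger readings are tempting, and the documents do not support them.

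- A reader might infer that prognostic factors are omitted 95% of the time, so that the adjusted result is usually unadjusted. The 95% applies to one covariate and only when it has no true interaction; step 4 shows omission falling to 75% and 36.5% under moderate interactions. The chance of an empty model is 0.95^k, which exceeds one half only up to 13 independent covariates, and the SAP does not fix the number.
- A reader might infer that 12.1.6 never adjusts for a prognostic covariate. The one-covariate models contain each of them whatever its p-value. What they lack is a clear overall adjusted hazard ratio, for the reason in step 6.
- A reader might infer the same defect in SAP 12.5.1, which says "Some of the suspected significant confounders are: age, time from symptom onset to randomization, African Americans, those previously taking aspirin" and adds index event type. That section uses another rule: univariate screening of suspected confounders, with stepwise selection optional. It shows that confounder-based adjustment is planned for the secondary outcomes. It does not supply an adjusted model for the primary outcome over the whole 90 days.

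**Conclusion.** The point holds as a mismatch between the aim of 12.1.6 and the rule it gives. The joint model is selected on effect modification, and the one-covariate models carry an interaction, so the section names no model that clearly gives an overall covariate-adjusted hazard ratio.

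For a covariate with no true interaction, omission is 95%. For the three named covariates, an empty joint model has probability about 86%, and for five about 77%, assuming independence and no interactions. The 3% precision figure depends on assumed covariate effects. The case for change therefore rests on clarity and pre-specification, not on power. The primary log-rank test, its alpha and the sample size are untouched. This is a modest point, worth correcting because the correction is nearly free.

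**What to change.** Replace the last sentence of SAP 12.1.6 with wording such as:

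*The adjusted analysis is one Cox model with treatment and pre-named baseline covariates (age, index event type, time from symptom onset to randomization, infarct on the initial scan, and any others chosen before unblinding from those listed in 12.5.1, such as race and prior aspirin use), all entered as main effects regardless of significance and without treatment interactions.*

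Keep the individual treatment-by-covariate interaction tests already in 12.1.6 and report them separately as effect-modification analyses. They should not be moved wholesale to the subgroup section: 12.1.8 specifies only tests of the treatment effect within subgroups at 0.05, so the p<0.10 step in 12.1.6 is the only interaction test stated for the main trial's primary outcome.

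The cost is SAP wording and a few degrees of freedom. With treatment, the four covariates and two more at one coefficient each, there are seven coefficients, or about 530/7 ≈ 76 planned events per coefficient. Every covariate proposed is already named in the SAP.

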# 12.1.7. Additional Efficacy Analyses of the Primary Outcome: On-Treatment Analyses (Secondary Analysis)

To account for study treatment discontinuations prior to 90 days, the primary efficacy outcome variable will be analyzed while on-treatment only, i.e., those who are known to have permanently discontinued the study drug will be censored one day after the date known to have permanently discontinued the study drug. Furthermore, this survival

POINT Trial Statistical Analysis Plan (Version 8: Sept 2017)

analysis of the composite events outcome will analyze all randomized subjects according to the treatment that they actually received (i.e., if they were assigned to receive study drug bottle containing drug A, but due to administrative/enrollment error, received a study drug bottle containing drug B, they would be analyzed with the group they actually received). For the interim analyses, to be included the subject must have been randomized at least 90 days prior to the data freeze.

The treatment effect in this analysis is tested at the two-sided alpha level of 0.05.

Likwise, the As-Treated analysis will be repeated for the primary and secondary efficacy and safety outcomes.

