3.1 Secondary

Several secondary analyses will be performed, including as treated analysis and evaluations of the impact of therapy on risk of the composite of major ischemic vascular events or major hemorrhage (primary outcome plus major hemorrhage), and on risk of major systemic or intracranial hemorrhage separately. Additional tertiary/exploratory analyses will include evaluation of the impact of therapy on: 1) ischemic stroke, 2) hemorrhagic stroke, 3) all-cause death, and 4) new handicap/disability. The impact of therapy on the composite outcome will also be evaluated in specific subject groups (e.g., African Americans, those previously taking aspirin, those with index TIA vs. minor ischemic stroke).

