7.4 Concurrent Treatment

7.4.1 Prohibited Concomitant Treatments

Use of the following medications after randomization and during the study period represents a protocol violation. However, if there is a clinical need that justifies the added risk of these interventions in the setting of study drug use, they should be employed at the discretion of the treating physician.

- NSAIDs, Cox1 inhibitors. If absolutely necessary, NSAIDs may be given for as short a time as possible but not sooner than 8 days after randomization
- Anticoagulants (both oral and parenteral, see listing on CRF 18)
- Open-label thienopyridines (e.g., ticlopidine, clopidogrel)
- Dipyridamole
- Other antiplatelets
- Thrombolytics (e.g., tPA)
- Vascular intervention (surgery and / or angioplasty of any vessel).

If intervention is absolutely necessary within the three months after randomization, study drug will be stopped 5 days prior to the intervention. Study treatment will then be restarted unless the subject needs to take open label clopidogrel or aspirin. In this case, study drug will be restarted only when treatment with open label antiplatelet therapy other than aspirin has been stopped.

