7.5 Treatment Discontinuation

The study drug should be continued whenever possible. If temporary interruption of study medication is required for surgery or other therapy, the subject's regimen will be resumed when it is considered safe by the subject's neurologist or primary care physician. Study medications will be restarted after carotid endarterectomy. If a clear indication for anticoagulation is revealed during the 90-day study period (atrial fibrillation, for example), study medications will be stopped and anticoagulation will be initiated.

If the study drug is stopped, it should be determined if the discontinuation can be made temporarily; permanent study drug discontinuation should be a last resort. Pregnancy will lead to definitive treatment discontinuation in all cases. In any case, all randomized subjects should remain in the study and followed per the protocol to 90 days from randomization, or to death, whichever comes first, even if the subject discontinues the POINT study drug regimen, unless the subject withdraws consent to participate in the trial.

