### 5 SAMPLE SIZE CONSIDERATIONS

### 5.1 Sample Size Determination for the primary efficacy Analysis

The minimum necessary sample size in the trial is established by the requirement to detect the smallest expected, clinically meaningful treatment difference comparing the treatment with placebo. A relative risk reduction of 23% is the smallest difference felt to be of clinical importance. The total sample size for the study is 4,150 subjects (rounded up from 4,142). With a sample size of 4,150 patients, with 530 events, the study will have 90% power to detect a relative risk reduction of 23% with a two-sided alpha of 0.05. The sample size was estimated based on a hazard ratio (HR) of 0.75 (equivalent to RRR of 23%) assuming an exponential survival distribution (assuming the proportion of patients with events in the placebo group is 0.1524 at 90 days), with inflation to account for two interim analysis for efficacy at equal intervals using O'Brien and Fleming stopping boundary using the Lan-Demets spending function and inflation for lost-to-follow-up and/or crossover. The intent-to-treat (ITT) principle is applied to the analysis, and therefore, we inflated the sample size to safeguard against lost-to-follow-up

and/or crossover in the actual treatment received, which may dilute the effect size. From FASTER there were 12% crossovers and 2% losses to follow-up [8]. Most events will occur early in the follow-up period and hence a smaller fraction of events will be lost and a smaller total correction in sample size is required (5.0%). Details regarding the sample size calculation are provided in Table 1.

Table 1. Assumptions and Specifications Used to Calculate Sample Size

| Proportion with events at 90 days in placebo (aspirin) group    | 15.24%  |
|---|---------|
| Relative risk reduction (reference: placebo+aspirin group)      | 0.23    |
| Hazard Ratio  | 0.75    |
| Delay between symptom onset and enrollment                      | 12 hour |
| Loss to follow-up at 90 days (from FASTER)                      | 2%      |
| Crossovers at 90 days (from FASTER, non-event related)          | 12%     |
| Impact of crossover on events                                   | 29%     |
| Inflation factor for crossovers and losses if events at 90 days | 31%     |
| Modeled inflation factor to account for crossovers/losses       | 5.0%    |
| Power   | 0.90    |
| Total alpha (2-sided) with 2 interim analyses                   | 0.05    |

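### The on-treatment analysis has no rule for open-label clopidogrel, so placebo patients who take it without a recorded permanent stop of study drug still count as on placebo

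*SAP*

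**What the plan says.** **The analysis.** Protocol 3.1 puts it among the secondary aims: "Several secondary analyses will be performed, including as treated analysis". SAP 12.1.7 states the purpose as follows: "To account for study treatment discontinuations prior to 90 days, the primary efficacy outcome variable will be analyzed while on-treatment only". The censoring rule is that "those who are known to have permanently discontinued the study drug will be censored one day after the date known to have permanently discontinued" study drug. Subjects are then analysed "according to the treatment that they actually received (i.e., if they were assigned to receive study drug bottle containing drug A", and the example continues with a subject handed the other bottle by mistake. The section is headed On-Treatment, but its last sentence says As-Treated. That sentence and SAP 12.5.1 repeat the analysis for the secondary efficacy, net-benefit and safety outcomes.

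**Open-label use.** Protocol 7.4.1 lists open-label thienopyridines, clopidogrel included, as prohibited, but allows them at the treating physician's discretion when clinical need justifies the risk. Where a vascular intervention leads to open-label treatment, "study drug will be restarted only when treatment with open label antiplatelet therapy other than aspirin has been stopped". Protocol 7.5 covers shorter gaps ("If temporary interruption of study medication is required for surgery or other therapy"), after which the regimen is resumed, and it discourages permanent stops. Protocol 7.5.1 does not list open-label antiplatelet use among the reasons for a permanent stop.

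**Crossover in the design.** SAP 5.1 says: "From FASTER there were 12% crossovers and 2% losses to follow-up". It links crossover in treatment received to a diluted effect. Because most events come early, it models a total correction of only 5.0%.

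**The concern.** Crossover is the departure that SAP 5.1 names as diluting the effect, yet the analysis built around treatment received has no rule for the drop-in part of it. The protocol steers sites toward holding and restarting study drug, so open-label use need not produce the one record that triggers censoring.

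The pathway is plausible. Protocol 2.6.3 reports clopidogrel plus aspirin in 14% and 23% of antithrombotic-treated TIA patients in two registries, and 25 polled sites (7 + 3 + 15) used it at least sometimes. These figures describe practice before the trial. They are not placebo-arm rates.

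For efficacy, the leftover bias is conservative. For major hemorrhage, the primary safety outcome, it is not: bleeds on open-label clopidogrel are credited to placebo and the excess looks smaller. Agreement between the ITT and as-treated bleeding results would then reassure more than it should.

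**Working it through.** **1. Who is censored under the present rule**

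| Placebo patient | Censored? |
|---|---|
| Study drug stopped for good and recorded as such | Yes, one day later |
| Open-label clopidogrel with study drug continued | No |
| Study drug held during open-label use, then restarted | No |
| Study drug held during open-label use, never restarted | Only if the site records a permanent stop; the SAP does not say |

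**2. The plan's own figures (SAP 5.1 and Table 1)**

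- Events: the Freedman formula at hazard ratio (HR) 0.75, 90% power and two-sided 0.05 gives 515. Solving the three-look Lan-DeMets O'Brien-Fleming design returns the Table 2 boundaries (3.710, 2.511, 1.993) and an inflation of 1.012, so 515 × 1.012 = 521, against 530 stated.
- Sample size: placebo risk 0.1524; active risk 1 - (1 - 0.1524)^0.75 = 0.1166; mean 0.1345. Then 530/0.1345 × 1.05 = 4,137, against 4,142 stated.
- Crossover impact if events fell at day 90: 1/(1 - 0.12)² = 1.291, the 29% in Table 1.
- Dilution implied by the 5.0% actually applied: 1 - 1/√1.05 = 0.024, or 2.4% of the log HR. The 5.0% also covers losses, so assigning all of it to crossover is generous.

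**3. Dilution left in the on-treatment HR**

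Assume open-label clopidogrel has the same HR of 0.75, and let x be the share of placebo event-weighted exposure spent on it. The placebo hazard is multiplied by (1 - x) + 0.75x = 1 - 0.25x, so the observed HR is 0.75/(1 - 0.25x). With 530 events the standard error of the log HR is about 2/√530 = 0.087. The shift in log HR is -ln(1 - 0.25x).

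| x | Observed HR | Shift in standard errors |
|---|---|---|
| 0 | 0.750 | 0 |
| 2.4% (from the 5.0% inflation) | 0.755 | 0.07 |
| 6% | 0.761 | 0.17 |
| 12% | 0.773 | 0.35 |

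The last row takes 12% as the placebo-arm rate, with every case a drop-in from day 0 and none recorded as a permanent stop. The on-treatment analysis will have fewer events than ITT, so its standard error is larger and the shift smaller in those units.

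**4. Bleeding, as an illustration**

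Protocol 2.4 cites mean major-bleeding rates of 1.7% on the combination and 1% on aspirin alone. If a share x of placebo exposure is on open-label clopidogrel, the ratio is 1.7/(1.0 + 0.7x): 1.70 at x = 0, 1.67 at 2.4%, 1.63 at 6% and 1.57 at 12%.

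**The case against.** The strongest reply is that 12.1.7 does what it says. Its stated aim is study-drug discontinuation, and it explains treatment received by the bottle. Censoring at open-label use targets a different estimand, in an analysis that SAP 9 treats as supportive and exploratory. That stands as a reason to add a version and keep the existing rule. It does not settle the matter, because the same analysis is called as-treated and is repeated for bleeding.

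Three limits on the pathway also stand. The hold-and-restart text in Protocol 7.4.1 concerns vascular intervention, not all open-label use. Protocol 5.2 excludes patients expected to need non-study antiplatelet drugs for more than 7 days. And open-label clopidogrel begun after a first primary event cannot change the time to that event, although the patient remains at risk for a later bleed.

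A reader might infer from the 12% that one placebo patient in eight will take open-label clopidogrel, and that the analysis therefore keeps all the planned crossover dilution and merely repeats ITT. The documents do not support this. The 12% has no stated drug, arm or direction, the pilot trial was a factorial test of clopidogrel and simvastatin (Protocol 2.4.3), and Table 1 calls the crossovers non-event related. Any part that is a recorded permanent stop, in either arm, is censored already.

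**Conclusion.** The gap is real and can be read from the text: drop-in without a recorded permanent stop remains as placebo time, and efficacy and bleeding contrasts move toward no difference. The effect is probably small for efficacy: HR about 0.755 instead of 0.750 at the level the SAP itself models, and 0.773 as an upper bound. Both figures assume that open-label clopidogrel works as well as study clopidogrel. Because no open-label rate for the placebo arm is given, the bias cannot be shown to be negligible, and for bleeding it runs in the unsafe direction. The primary ITT test and the sample size are untouched. This is a worthwhile, inexpensive improvement to a secondary analysis, not a flaw in the trial's main inference.

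**What to change.** In SAP 12.1.7, before unblinding:

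- Add an on-treatment analysis that censors at the earlier of (a) one day after permanent discontinuation of study drug and (b) first recorded use of an open-label thienopyridine, other non-aspirin antiplatelet or anticoagulant, in either arm, whether or not study drug is held. The anticoagulant trigger will largely coincide with (a), since Protocol 7.5.1 already lists that indication as a reason to stop.
- Report it beside ITT and the existing 12.1.7 rule.
- For this analysis, class a hold that is never resumed as a permanent stop from the date of the hold.
- Apply it to the secondary and safety repeats in 12.1.7 and 12.5.1.
- Use one name for the analysis throughout.

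Take dates from the concomitant-medication form and the protocol-violation record; Protocol 8.6 already makes receipt of a prohibited medication a major violation. First confirm that start dates are captured: Protocol 1.2 schedules the form only at day 7, day 90 and event visits.

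The cost is SAP wording, programming and slightly fewer events. Open-label treatment may be prompted by a TIA or a procedure, so the added censoring may be informative, as censoring at discontinuation already can be. That is why the three analyses should be read together.
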